Phase I Data analysis strategy: Baseline participant characteristics as well as assessment items (quantitative and qualitative) used to assess acceptability and feasibility of the intervention will be analyzed using descriptive statistics (quantitative data) and thematic coding (qualitative data). We will conduct a longitudinal analysis from baseline across 3- and 6-weeks to examine changes in i) intentions to seek HTC; ii) rates of HTC; and iii) knowledge about HIV/AIDS. In general, we will use two-tailed tests and p-values smaller than 0.05 will be considered to indicate statistical significance. When necessary, however, we will use appropriate adjustment of

the level of significance (alpha) to account for multiple statistical tests. All of these analyses will be exploratory given the study sample size. Findings from these analyses in combination with the acceptability and feasibility assessments will be critical in informing the sample size needed to provide power to detect significant differences between the game and a control condition in a subsequent full-scale randomized trial to be conducted through a Phase II proposal. The product and data that result from this Phase I project will be used to prepare a Phase II STTR application.

Phase II Data analysis strategy: All statistical analyses will be conducted based on the “intent-to-treat” principle, through the use of either SPSS or SAS statistical packages.

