Statistical analyses: **Primary outcome:** Due to COVID-19’s impact on this study’s initial primary outcome of the number of participants that were tested for HIV at the 6 month timepoint, the primary outcome has been modified. Behavioral outcomes are influenced by attitudes and intentions; therefore, we will explore attitudes and intentions in our study, with **attitudes about around HTC** as the new primary outcome. After a thorough review of existing literature, the team decided that the primary outcome would be changed to measuring participant’s attitudes around HTC at 6 months for the full cohort, with intentions and behaviors being assessed as secondary outcomes. **Secondary outcomes:** To address the secondary outcomes we will use repeated measures ANCOVAs (with Bonferroni corrections to account for multiple statistical tests). The models will include attitudes, perceived barriers, perceived norms, intentions, self-efficacy, and knowledge as dependent variables, with study condition as the independent variable, and sex, ethnicity, and history of testing as covariates. **Mediators and moderators:** Data will be collected on potential mediators and moderators and examined using conventional methods¹¹³. Baseline levels of these mediators and moderators will be used in the models to assess whether these variables affect the primary or secondary outcomes. In addition, because these variables might change over time during participation in the study, they will also be considered as time-varying covariates. **Mediators:** Based on our logic model¹² that will guide the development of the proposed intervention, we predict that 1) attitudes, 2) perceived barriers, 3) perceived norms, 4) intentions, 5) self-efficacy, and 6) knowledge will mediate the effects of the intervention on HTC at 6 months. The selection of mediators is based upon the logic model and given the proposed game will have many different components (as our current *PlayForward* game does), and given our experience of including all of these components into a game intervention, this selection of mediators was carefully guided by the process of constructing the logic model. We will use the criteria proposed by Baron and Kenny (1986)¹¹³ to test the relationships among the outcomes and presumed mediators. According to these criteria, four conditions should be met to establish mediation. We outline these conditions using our specific hypothesis that intentions mediate the relationship between the study condition (intervention or control) and HTC as an example. The first condition is that the study condition is directly related to HTC. Second, the intervention condition has a direct effect on the mediator (intentions). Third, intentions have a direct effect on HTC, when the study condition is controlled. Fourth, if intentions mediate the intervention condition-HTC relationship, the direct effect of the study condition on HTC is reduced or eliminated after controlling for intentions. To test the significance of mediation effect, which is called indirect effect, we will calculate Sobel's test¹¹⁴⁻¹¹⁶ for each proposed mediator. Sobel's test determines the significance of the mediation effect by testing the null hypothesis that the indirect effect coefficient is zero (i.e. whether the indirect effect of the independent variable on the dependent variables is significantly different from zero). **Moderators:** Variables that predict the outcome variable (first substance use) differently between treatments will be considered to be moderators using the model outlined by Kraemer et al¹¹⁷. In order to be considered a moderator, the variable must be present prior to randomization and must not be related to the independent variable (*PlayTest!* vs. control games). Pre-randomization variables that interact with the independent variable in predicting the outcome variable (HTC) will be considered moderators of treatment. Variables that predict the outcome variable but do not significantly interact with treatment condition will be classified as nonspecific pre-randomization predictors.

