
Collection and analysis of the in-game data: We will build on systems we have developed to analyze the data collected by the game software or the in-game data⁹⁸, which will serve as the foundation for analytics system built into the game. Briefly, using Player Game State Data (the traditional save/load data so a player can save their progress and pick up later where they left off) and Activity Logging Data (the relevant time-stamped player

actions during gameplay), we will examine the paths taken and decisions made by each player, documenting their exposure to content and the “learning curve” from the in-game data.

All data collected from the assessments will be entered directly into the secure web-based system, OnCore, Yale’s enterprise-wide clinical research management system. OnCore is a fully integrated system development by Forte, which includes three modules: 1) Clinical research management (CRM); 2) Bio-specimen management (BSM); and 3) Patient registry. This project will utilize the CRM module as the electronic data capture system for all case report form data and to support subject tracking. Data will be entered into the OnCore system either by research staff, or with the more sensitive assessments, by the participant themselves. This method limits data entry-associated errors. Before enrolling participants into the intervention, we will conduct a pilot test with two to three participants to assess acceptability and usability of the game, make changes as needed, and confirm data collection procedures.

New proposed plan for analysis approach due to COVID-19

1. Revise power calculations to ensure that a clinically meaningful effect size for the new primary outcome (attitudes around HTC at 6 months in the full cohort) can be detected.
2. Examine **attitudes** around HTC as primary outcome at 6 months in the full cohort.
3. Examine **intentions** to get tested at 6 months in full cohort.
4. Examine **HTC** at 6 months in smaller cohort of students that were able to reach the full 6 months of the study without being impacted by the pandemic (N=135). This study is not powered to detect a difference at this smaller sample size.

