5. Examine **HTC** at 3 months for a sub-cohort of students who were able to reach that time point without being affected by the pandemic (N=237; the study is powered for this outcome at n=236, but at 6 months). While we technically would be powered at this time-point, we would have cut our time to reach the outcome in half, posing a considerable limitation.
6. Examine attitudes and intentions at 3 months (N=237) (to be used in conjunction w #4 directly above).

New data analysis plan suggestion from study's Data Safety Monitoring Board member

- Use mixed models for the repeated measures analyses of the dimensional outcomes, as they use all available data on an individual and are generally robust to data missing at random. The repeated measures ANOVA approach that is mentioned in the document is meant for complete data and is not flexible in accounting for the correlations within individual.

SECTION II: RESEARCH INVOLVING DRUGS, BIOLOGICS, RADIOTRACERS, PLACEBOS AND DEVICES

If this section (or one of its parts, A or B) is not applicable, check off N/A and delete the rest of the section.

A. RADIOTRACERS

N/A

1. Name of the radiotracer: *Write here*
2. Is the radiotracer FDA approved? YES NO

If NO, an FDA issued IND is required for the investigational use unless RDRC assumes oversight.

3. Check one: IND# *Write here* or RDRC oversight (RDRC approval will be required prior to use)

B. DRUGS/BIOLOGICS

N/A

1. If an **exemption from IND filing requirements is** sought for a clinical investigation of a drug product that is lawfully marketed in the United States, review the following categories and complete the category that applies (*and delete the inapplicable categories*):

Exempt Category 1: The clinical investigation of a drug product that is lawfully marketed in the United States can be exempt from IND regulations if all of the following are yes:

1. The intention of the investigation is NOT to report to the FDA as a well-controlled study in support of a new indication for use or to be used to support any other significant change in the labeling for the drug.	
2. The drug that is undergoing investigation is lawfully marketed as a prescription drug product, and the intention of the investigation is NOT to support a significant change in the advertising for the product.	

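### Section 13 makes month-6 attitudes the primary outcome, but the only analysis it states for attitudes is the Bonferroni-corrected secondary one, and Sections 4 and IV still name HTC as primary

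*Combined protocol and SAP*

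**What the plan says.** Section 13 (Statistical Considerations, Phase II, Primary outcome) says that because of COVID-19 "the primary outcome has been modified". Attitudes around HTC at 6 months in the full cohort becomes primary, "with intentions and behaviors being assessed as secondary outcomes". Item 2 of the new proposed plan in the same section repeats this: attitudes "around HTC as primary outcome at 6 months in the full cohort".

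The Secondary outcomes text comes next. It specifies repeated measures ANCOVAs "with Bonferroni corrections to account for multiple statistical tests" and continues: "The models will include attitudes, perceived barriers, perceived norms, intentions, self-efficacy, and knowledge as dependent variables". The same sentence stands in Section 4 (Research Plan, Data analysis), where HTC is the primary outcome.

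Section 4 still defines the primary outcome as the proportion obtaining HTC within six months, compared by Fisher's exact test at two-sided 0.05. The data-collection text in Section 4 and item 2 of Section IV (Confidentiality & Security of Data) also describe HTC as the primary outcome.

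The only significance level inside Section 13 is in the Phase I paragraph, where "p-values smaller than 0.05 will be considered to indicate statistical significance".

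**The concern.** A primary outcome needs one stated test at one stated level. Here attitudes has been promoted to primary without being taken out of the secondary family. The sentence giving Fisher's exact test at 0.05 was dropped from Section 13 together with the old primary, and nothing took its place. An analyst who follows Section 13 as written finds one analysis for attitudes as an outcome, and it carries a multiplicity penalty meant for secondary outcomes. An analyst who follows Section 4 finds a different primary outcome.

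What is at stake is whether a given month-6 difference in attitudes counts as a positive trial, and how much power the trial has for the outcome it now rests on. Item 1 of the new proposed plan promises revised power calculations for attitudes. Those calculations cannot be done until a level is fixed.

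**Working it through.** **The texts side by side**

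| Place | Primary outcome | Test and level for it |
|---|---|---|
| Section 4, Data analysis | HTC within six months | Fisher's exact, two-sided 0.05 |
| Section 4, Data collection and management | HTC | none given |
| Section IV, item 2 | HTC | none given |
| Section 13, Primary outcome | Attitudes, 6 months, full cohort | none given |
| Section 13, Secondary outcomes | Attitudes listed first of six | Repeated measures ANCOVA, Bonferroni, no divisor |
| Section 13, new proposed plan, items 1 and 2 | Attitudes, 6 months, full cohort | none given |

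No divisor is stated. Counting one test per variable, it could be 6 (the list as it stands), 5 (attitudes removed) or 7 (HTC added, since behaviors are now secondary but are not in the list).

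**The plan's own numbers.** The sample-size paragraph in Section 4 requires 118 per group and allows for 20% dropout: 118 / 0.80 = 147.5, rounded up to 148 per arm, or 296 in total. That step reproduces. The 118 was set for HTC rates from an effect size of 0.27 whose metric is not stated. Read as a standardized mean difference at two-sided 0.05 and 85% power, 0.27 would need 247 per arm. The present point does not depend on that.

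**Illustration of the gap between the two levels**

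Assumptions: divisor 6, so alpha is 0.05 / 6 = 0.00833; an unadjusted two-group t-test; 118 per arm (the HTC planning number) to 148 per arm (all 296 observed). The number with month-6 attitudes data is not given.

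Smallest observed difference reaching significance, in SD units = critical t × sqrt(2/n).

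| n per arm | df | sqrt(2/n) | Critical t at 0.05 | Difference | Critical t at 0.00833 | Difference | Ratio |
|---|---|---|---|---|---|---|---|
| 118 | 234 | 0.1302 | 1.970 | 0.26 SD | 2.661 | 0.35 SD | 1.35 |
| 148 | 294 | 0.1162 | 1.968 | 0.23 SD | 2.656 | 0.31 SD | 1.35 |

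Example: an observed 0.30 SD gives t = 0.30 / 0.1302 = 2.304, p = 0.022 with 118 per arm, and t = 2.581, p = 0.010 (0.0103) with 148 per arm. Both pass at 0.05 and fail at 0.00833. They also fail with a divisor of 5 (0.01) or 7 (0.00714).

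Power cost, by normal approximation: a true effect of (1.960 + 1.036) × sqrt(2/118) = 0.390 SD has 85% power at 0.05 with 118 per arm. At 0.00833 the critical z is 2.638, so power is Φ(0.390 / 0.1302 − 2.638) = Φ(0.358), or 64%.

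**The case against.** Section 13 is explicit that attitudes replaced HTC, gives the reason, and repeats the decision in its new proposed plan. A coherent reading is also available. The month-6 contrast is primary and uncorrected, while attitudes in the secondary list means its course over time or its value at 3 months, which item 6 of the new plan does examine. The only levels printed anywhere are 0.05; no divisor and no 0.0083 appears. These points stand, and they limit the seriousness of the problem. They do not remove it, because the text never states that reading, and a sentence unchanged from the plan in which HTC was primary cannot have been written to draw the distinction.

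A reader might infer that the trial now has two competing primaries and inflated error: two independent tests at 0.05 would give 1 − 0.95² = 0.0975. The documents do not support that, because Section 13 replaces HTC and does not add to it. A reader might also infer that an unwritten threshold lets the sponsor raise the error rate by choosing late. Both candidate levels are at or below 0.05, so choosing between them cannot take a given attitudes test above 0.05.

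HTC is not without a plan either. Section 13 examines it at 6 months in 135 participants, where "This study is not powered to detect a difference at this smaller sample size", and at 3 months in 237, noting that "the study is powered for this outcome at n=236, but at 6 months". Its test is missing from Section 13 but is available in Section 4. That gap, the unstated divisor and the choice between the two attitudes rows in Table 1 are mainly missing detail.

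**Conclusion.** The plan is wrong as written and should be fixed, but this is not a defect that undermines the trial. Month-6 attitudes is named primary while the only analysis stated for it is a Bonferroni-corrected secondary one, and live text in Sections 4 and IV still names HTC as primary. Taken literally, the primary is tested below 0.05. The bar then rises by a factor of about 1.35, and an effect with 85% power at 0.05 has about 64%. These figures are illustrative. They rest on an assumed divisor of 6, an unadjusted t-test that is not the planned model, and 118 to 148 per arm, where 118 is an HTC planning number and not an established floor for attitudes data. The harm is lost power and an ambiguous success criterion, not type I error inflation.

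**What to change.** 1. In Section 13, state that the between-arm contrast in attitudes around HTC at 6 months is the single primary test, at two-sided 0.05, outside the Bonferroni family.
2. Take that contrast out of the secondary list. Attitudes at other visits may stay as labelled secondary analyses. Set the divisor to the number of secondary tests actually listed.
3. Estimate the primary contrast with the mixed model that Section 13 already records as a suggestion from a monitoring board member, adjusted for baseline attitudes, sex, ethnicity and history of testing. It uses all available visits, whereas the repeated measures ANCOVA now written needs complete data.
4. In Section 4, replace the HTC-primary analysis text and the data-collection wording, and do the same in Section IV. Move HTC to secondary with its Fisher's exact test, keeping the statement that the month-6 analysis in 135 participants is not powered.
5. Have the sponsor confirm, before outcomes are compared by arm, which of the two attitudes rows in Table 1 (HIV, or STI and HIV testing) is the primary measure.

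The cost is wording and minor analysis work, with no new data, visits or participants.

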PlayForward videogame¹², we will use our newly refined conceptual model and the data from the focus groups to inform expanded intervention manuals (“Game PlayBooks”). These Game PlayBooks will be used as working documents between the research team members throughout the Phase II project. In these documents, the theory-based behavior change components are outlined alongside the game design elements. Our manuals from our previous intervention will be updated to include all components for our focus on HTC. From these manuals and subsequently developed storyboards, we will produce adapted and new components of the game to be built into the web-based system and tested in Stage 2 of the study. Going into Stage 2 of Phase II for this protocol, we will also work with partners to further execute strategies for widespread distribution of the adapted game.

Conduct individual interviews with stakeholders (n=15): To further assist with creating new storylines and content for the web-based version of the game, we will conduct qualitative semi-structured one-on-one interviews with key stake-holders (i.e. school administrators, counselors, teachers, nurses, site coordinators, and community partners).

Stage 2: Randomized controlled trial of the *PlayTest!* videogame (Aim 3)

Design: We will enroll 296 girls and boys who attend one of our partner programs. Eligible individuals will be assigned to either the ***PlayTest!*** arm (n=148) or a set of attention/time control games (n=148). All participants will play one to two sessions per week for four weeks for a goal of 5 hours of gameplay, which will take place through the web-based game. All gameplay will occur on site at their programs. This total duration and number of sessions is consistent with those found in effective HIV prevention interventions, with the amount of time adolescents play games³⁶, and the amount of gameplay observed among participants in the ***PlayForward*** study⁹⁷. We will collect follow-up data on all participants at four weeks (immediately following completion of gameplay), three and six months.

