Adequacy of sample size: A sample size calculation was done using the G*Power software. An effect size of 0.27, was estimated (conservatively) based on previous research¹⁰³. With equal numbers of subjects in each group, and alpha = 0.05, to provide 85% power to detect a difference in HTC rates at six months controlling for history of testing, sex, and ethnicity, a sample of 118 per group (total N = 236) is required. Based on adherence rates from our test of the original ***PlayForward*** game we assume 80% retention at 6 months. To account for the 20% dropout we will seek to enroll 296 participants.

Randomization: We will use a stratified randomization procedure¹⁰⁴ to assign participants to one of the study arms. Gender, race/ethnicity, and age will be included in the randomization algorithm because these variables have been found to be important predictors of HTC in adolescents¹⁰³. The stratification would be as follows two gender groups (girl vs. boy), two ethnic groups (Hispanic vs. non-Hispanic), three groups for race (White, African-American, Other) and two groups for age – (14, 15, 16 vs. 17 and 18). A block size of 6 will be used for the stratification process.

Treatment conditions: The research staff will orient the participants to the use of either ***PlayTest!*** or the control videogames. Players in both groups will play through an online tutorial demonstrating the mechanics of the game. Each player will use a dedicated device to access their game on the web and a set of headphones that they will use during each gameplay session. The research staff will oversee all gameplay to ensure that participants are playing and to field any questions. The control videogames (**see below**) will be engaging and fun but will be devoid of relevant content.

Assessments: We will assess participant characteristics (demographic), outcomes, and process measures (Table 1). For outcomes, we will collect data on actual HTC and assess a variety of mediators and moderators among teens (e.g., attitudes, intentions, knowledge). To measure actual testing in our participants, we will work with health care professionals at school clinics located on the premises of our partner sites to determine if students who participated in our study subsequently got tested. This data will be collected based on the protocol of the specific clinic, and the participants’ personal health information will be de-identified (including results) before being

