- ⊕ At the end of each month, the facilitator will check the *Student Identification Form* to identify any students that have utilized the school based health center during that month.
 - If a student has used the health center, then the facilitator will record pertinent information on the *Health Center Participation Form* that is on the password protected excel document for the monthly time period in review.
- ⊕ At the end of each month, the facilitator will meet with a member of the play2PREVENT team for approximately 10-15 minutes. During this brief meeting the SBHC facilitator and the play2PREVENT team member will print the *Health Center Participation Form* for the time period at hand and both parties will sign-off on its completeness. The printed sheet will then be placed in the secured lockbox with the USB drive.
- ⊕ Use the 3000z billing code for participants that come in for a STI/HIV test to protect privacy during insurance billing.

Data analysis

Phase 2: Data analyses general considerations: All statistical analyses will be conducted based on the “intent-to-treat” principle, through the use of either SPSS or SAS statistical packages.

Statistical analyses: **Primary outcome:** The primary outcome will be the proportion of participants who engage in HTC within the six-month study period. Rates of HTC among intervention and control participants at six months will be compared using Fisher’s exact test and a 2-sided test at the 0.05 level. **Secondary outcomes:** To address the secondary outcomes we will use repeated measures ANCOVAs (with Bonferroni corrections to account for multiple statistical tests). The models will include attitudes, perceived barriers, perceived norms, intentions, self-efficacy, and knowledge as dependent variables, with study condition as the independent variable, and sex, ethnicity, and history of testing as covariates. **Mediators and moderators:** Data will be collected on potential mediators and moderators and examined using conventional methods¹¹³. Baseline levels of these mediators and moderators will be used in the models to assess whether these variables affect the primary or secondary outcomes. In addition, because these variables might change over time during participation in the study, they will also be considered as time-varying covariates. **Mediators:** Based on our logic model¹¹² that will guide the development of the proposed intervention, we predict that 1) attitudes, 2) perceived barriers, 3)

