Phase I: 4 focus groups of 5 adolescents each (n = 20), boys and girls, aged 15-18 will participate in the focus groups and 30 adolescents, boys and girls, aged 15-18 will participate in the pilot testing of the adapted game. These adolescents will be recruited from the school-based or after-school programs, or community youth programs that we already have established partnerships with, such as LEAP, Hamden Youth Center, and the local public library.

Phase II: Recruitment/enrollment for this portion of the project (including focus groups and the RCT) will take place at one of the community high school programs, youth programs, or local health programs with which we already have partnerships (see Letters of Support). Our team has a successful track record of establishing a consistent presence at our partner sites and now has close working relationships with the program staff that are fully engaged in the recruitment process. Sites for recruitment and participation include but are not limited to: Wilbur Cross High School, the Leadership, Education, & Athletics in Partnership (LEAP) Program, Hillhouse High School and Planned Parenthood of Southern New England (PPSNE).

7. **Subject classification:** Check off all classifications of subjects that will be specifically recruited for enrollment in the research project. Will subjects who may require additional safeguards or other considerations be enrolled in the study? If so, identify the population of subjects requiring special safeguards and provide a justification for their involvement.

 Children	 Healthy	 Fetal material, placenta, or dead fetus
 Non-English Speaking	 Prisoners	 Economically disadvantaged persons
 Decisionally Impaired	 Employees	 Pregnant women and/or fetuses
 Yale Students	 Females of childbearing potential	

NOTE: Is this research proposal designed to enroll children who are wards of the state as potential subjects?

Yes No

8. **Inclusion/Exclusion Criteria:** What are the criteria used to determine subject inclusion or exclusion?

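### Adding site to the attitude and other questionnaire models would be a cheap, small gain in precision; leaving it out does not bias the comparison

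*Combined protocol and SAP*

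**What the plan says.** **Sites and delivery.** Item 6 (Subject Population) says "Sites for recruitment and participation include but are not limited to" two high schools, a youth program and a health organisation. The Phase II Stage 2 design in item 4 states "All gameplay will occur on site at their programs". The Stage 2 data collection text also refers to health centers at partner sites in the plural.

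**Randomisation.** Item 4 assigns individuals, stratified by gender, ethnicity, race and age group, in blocks of 6. Site is not a factor.

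**Analysis.** Item 13 makes six-month attitudes the primary outcome. It also lists attitudes with perceived barriers and norms, intentions, self-efficacy and knowledge in repeated measures ANCOVAs "with study condition as the independent variable, and sex, ethnicity, and history of testing as covariates". The primary outcome has no covariate list of its own. HTC is assigned Fisher's exact test in item 4, as "a 2-sided test at the 0.05 level", without covariates. The COVID-19 analysis plan and the mixed-model suggestion from a monitoring board member, both at the end of item 13, do not mention site.

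**Sample size.** Item 4 reads "An effect size of 0.27, was estimated (conservatively) based on previous research" and "With equal numbers of subjects in each group, and alpha = 0.05", and aims "to provide 85% power to detect a difference in HTC rates at six months controlling for history of testing, sex, and ethnicity". The result is 118 per group. Site plays no part in it.

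**The concern.** Participants at one school or program share a setting, a student body and supervised play sessions, so their questionnaire scores may be more alike than scores from different sites. If so, a model without site counts that shared variation as noise, and the standard error of the arm difference is larger than it need be. Because allocation is not balanced by site, one arm may also by chance hold more participants from a high-scoring site, and the model has no term to correct for it. At stake is some precision for the new primary outcome and the other questionnaire outcomes.

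**Working it through.** **1. The plan's own figure.** Inputs from item 4: two-sided alpha 0.05, power 85%, effect size 0.27 (metric not stated), 118 per group. Read as a standardised mean difference:

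n per arm = 2(z₀.₉₇₅ + z₀.₈₅)²/d² = 2(1.960 + 1.036)²/0.27² ≈ 247 (one-sided: 198).

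Read as Cohen's f (one numerator df) or w (one df), 0.27 needs 126 or 124 in total. None of these gives 118 per group. The dropout step does reproduce: 118/0.8 = 147.5, so 148 per arm and 296 in total. The mismatch is a separate matter. To keep the plan's 118 and 85%, I solve for the effect instead: d = (1.960 + 1.036)·√(2/118) = 0.39. This serves only as a benchmark, because the calculation was made for HTC and the power for attitudes is still to be revised.

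**2. Gain from adjustment.** Let ρ be the share of outcome variance lying between sites. It is an assumption; the documents give no value. In outcome-SD units, with n = 118 per arm:

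- variance of the arm difference without site: 2/n; with site: 2(1 − ρ)/n
- power = Φ(0.39/√(2(1 − ρ)/n) − 1.96)
- participants gained ≈ 236ρ
- SD of the arm difference due to chance site imbalance = √(2ρ/n)

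| ρ (assumed) | Variance cut | SE without → with site | Power without → with site | Worth, of 236 | Imbalance SD |
|---|---|---|---|---|---|
| 0.01 | 1% | 0.1302 → 0.1295 | 85.0% → 85.3% | about 2 | 0.013 |
| 0.05 | 5% | 0.1302 → 0.1269 | 85.0% → 86.7% | about 12 | 0.029 |
| 0.10 | 10% | 0.1302 → 0.1235 | 85.0% → 88.5% | about 24 | 0.041 |

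**3. Validity without site, by simulation.** Assumptions: 6,000 trials per scenario, N = 236, four sites holding 40/30/20/10% of participants, individual 1:1 allocation ignoring site.

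| ICC | Type I error without / with site | Power without / with site |
|---|---|---|
| 0.01 | 4.9% / 5.0% | 84.7% / 84.4% |
| 0.05 | 5.4% / 5.2% | 84.7% / 85.6% |
| 0.10 | 5.6% / 5.2% | 85.9% / 87.9% |

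The Monte Carlo standard error at 5% is √(0.05·0.95/6000) ≈ 0.3 points, so there is no material inflation.

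The simulated power gains are smaller than those in step 2 for two reasons. With these site shares, only 1 − (0.4² + 0.3² + 0.2² + 0.1²) = 0.70 of the assumed between-site variance appears within a trial on average. Estimating three site terms also costs about 3/235 ≈ 1.3% in variance. Step 2 is therefore the favourable end, and at ICC 0.01 the gain is roughly nil.

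**The case against.** The strongest reply is that nothing is broken: allocation is individual, and choosing one more covariate is a matter of preference. That stands in full as regards validity. A reader might infer from the missing site term that the comparison is biased or its p-value unreliable, but the design and step 3 do not support this.

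A reader might also infer that differences in clinic recording distort the quoted models, since item 4 says of the testing data "This data will be collected based on the protocol of the specific clinic". They do not. Those models cover questionnaires that participants enter themselves; clinic records bear on HTC, which is now secondary and has a different test. Even for HTC, item 4 gives the health centers one common form, a monthly check and a joint monthly sign-off.

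The site structure is also uncertain. Item 6 speaks of recruitment at one of the programs before listing several, the list covers focus groups as well as the trial, and trial entry requires enrolment in a school's clinic. Several sites is the natural reading, but the number of trial sites and their sizes are unknown.

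Finally, the benefit may be small. Item 13 also brings baseline levels of the mediators, attitudes among them, into models. If that applies to the primary analysis, baseline attitudes may absorb much of any stable site difference. This is fair, and it is why low ICC values belong in the range. What remains is that a design feature known before randomisation appears in no planned model, while the plan is already under revision.

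**Conclusion.** The point holds as an optional improvement of low severity. Site is absent from the randomisation factors and from every stated analysis, and for the questionnaire outcomes the consequence is lost precision only. For assumed ICCs of 0.01 to 0.10 the variance reduction is about 1% to 10%, worth about 2 to 24 of 236 participants, with power at 118 per arm reaching about 85.3% to 88.5% instead of 85.0%. Allowing for the cost of estimating the site terms, the gain is somewhat less, and about zero at the bottom of that range. Chance site imbalance moves the estimate with an SD of 0.013 to 0.041 outcome SD, against a benchmark effect of 0.39. All these figures rest on assumed ICCs, and the simulated ones also on assumed site shares. The documents support neither a claim of bias nor a claim that the added precision costs nothing.

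**What to change.** In the revised analysis plan, add site as a fixed effect to the model for six-month attitudes and to the other questionnaire models, whether these stay as ANCOVAs or become mixed models. State the rule for pooling small sites and settle it before unblinding, so that it cannot look like a choice made after the results. With perhaps four sites, a random intercept would rest on a poorly estimated variance, so fixed effects are preferable.

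For HTC, keep Fisher's exact test, which takes no covariates. Add a Mantel-Haenszel or exact analysis stratified by site, labelled supportive. The sub-cohorts of 135 and 237 could be too sparse for site fixed effects if few participants are tested.

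Leave randomisation unchanged. The present factors give 2 × 2 × 3 × 2 = 24 strata, about 12.3 participants each at 296. Crossing them with four sites (assumed) would give 96 strata of about 3.1, below one block of 6.

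The cost is a short addition to the plan, a few degrees of freedom and the pooling rule. No new data collection is needed, since participants enrol and play at their site.
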